2. To assess the effects of the NMDA antagonist, memantine, on PPI and neurocognition in healthy subjects, and the moderating roles of personality and genotype in these effects. 30 healthy subjects will complete a within-subject study of placebo vs. 20 mg memantine (p.o.) on two separate days, completing measures of sensorimotor gating and neurocognition on each test day. All subjects will be characterized in terms of specific genetic and personality characteristics.

3. To assess the effects of the NMDA antagonist, memantine, on PPI and neurocognition in schizophrenia patients, and the moderating roles of genotype in these effects. 60 well-characterized and clinically stable individuals with schizophrenia will complete a within-subject study of placebo vs. 10 mg memantine (p.o.) (n=30) or placebo vs. 20 mg memantine (n=30) on two separate days, completing measures of sensorimotor gating and neurocognition on each test day. All subjects will be characterized in terms of specific genetic characteristics.

BACKGROUND AND SIGNIFICANCE 7.

The startle reflex is a constellation of responses to sudden, relatively intense stimuli that is usually classified as a defensive response. One major advantage of startle response paradigms is that the same phenomena can be studied across species. In humans, the blink reflex component of the startle response is measured using electromyography of the orbicularis oculi muscle. Despite its simplicity, startle demonstrates several forms of plasticity - including habituation and fear-potentiation - that are regulated by forebrain circuitry. Even these more complex processes exhibit striking similarities across species, from rodents to humans. One form of startle plasticity is "prepulse inhibition" (PPI), which is the normal suppression of the startle reflex, which occurs when the intense startling stimulus is preceded by a weak prestimulus.

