d) Subject payment (also see below, section 18): For subjects participating in the "Within-Subject" test sessions, payment will be divided in the following schedule: on completion of screening day: \$30; on completion of first TEST SESSION day: \$100; On completion of second TEST SESSION day: \$130. This payment schedule provides appropriate incentive for the subjects to return for the second test day. This is to ensure that subjects return for the second and third test days. If subjects fail screening criteria for recreational drug use prior to any TEST SESSION day, they will not be tested further and will not be paid for that test day. We will recommend that subjects remain in our laboratory for monitoring until six and one half hours after pill ingestion. Should they choose to leave our facility for any reason prior to that time, it will be at their own risk. Their involvement in the study will be completed and payment on the Test Session day will be prorated to \$16 per hour.

e) Venopuncture: Venopuncture for COMT allelic testing in some subjects will occur during the initial visit, before or after what normally is titled the SCREENING SESSION in the studies listed below. A single venopuncture performed by certified individuals within the UCSD Medical Center GCRC/CTRI or Blood Drawing Station will be used to 10 cc of blood for COMT allelic testing. Based on specific needs of the experimental design (e.g. equal number of Met/Met, Val/Met and Val/Val allelic carriers, or subgroups of "high" vs. "low" PPI levels, based on the upper vs. lower quartile of a normal population distribution), subjects may be asked to come back for further testing, if they indicate they would like to do so. If participants continue to the remainder of the study, there will be 2 test days, one of which will involve placebo, and the other day involving an active dose of amphetamine (20 mg), memantine (20 mg) or other approved test drug/dose. The TEST SESSIONS will mimic those in the WITHIN-SUBJECT model below; however, venopuncture occurs only during the first visit.

f) Clinical assessment: Specific clinical assessment tools used in control and schizophrenia subjects are described in Section 10.

g) Test schedules:

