Lastly, based on the impact of basal PPI level and personality measures in controls, we hypothesize that a critical moderating factor underlying PPI memantine sensitivity is COMT Val158Met genotype; specifically, we predict that "Val/Val" individuals will be most sensitive to memantine-enhanced PPI. This will be tested in two ways: first, by ANOVA as above, with COMT status as a between-subject factor, and memantine dose and prepulse interval as within-subject factors. Significant genotype x dose or genotype x dose x int interactions, with appropriate post-hoc comparisons, would confirm the hypothesis. Estimating d=1.53, based on the mean "d" of two "COMT phenotypes" in controls - low basal PPI (d=1.80) and high "novelty seeking" personality (d=1.27) - the proposed 11 Val/Val and 7 Met/Met patients/dose group would yield power of 0.90 to detect genotype-sensitive memantine effects. It is possible that various factors (including a skewed distribution of allele frequencies, or substantial genotype effects on basal PPI levels) might preclude detection of a significant 2- or 3-way interaction. A secondary (albeit weaker) test of the hypothesis will utilize separate ANOVAs in Val/Val vs. Met/Met subgroups, with predicted PPI-enhancing effects of memantine in the Val/Val but not Met/Met subgroups. Previous reports also predict a significant main effect of genotype, with PPI levels following the Met/Met>Val/Met>Val/Val gradient. Logistic regressions might be used, with genotype coded to reflect "dose" of the Met allele (Val/Val=0, Val/Met=1, and Met/Met=2), to assess the distribution of the neurophysiological and neurocognitive measures. All analyses will be conducted independently for each dose group. If comparable effects are evident with 10 and 20 mg doses, dose groups may be pooled to increase power for exploratory analyses (e.g. to detect genotype x drug effects).

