Main effects of memantine on WM will be tested by one-way ANOVA with memantine dose as a withinfactor. Based on d=0.73 for increased WM after 20 mg MEM in controls (see above), the proposed 30 patients/dose group would yield power of 0.79 to detect significant WM-enhancing effects. While preliminary data yield less robust predictions for COMT subgroup sensitivities in memantine effects on WM performance, given the significant correlation of WM and PPI, and known impact of COMT genotype on PPI levels, we predict some differential (Val/Val > Met/Met) memantine sensitivity in this measure. If we estimate effects of COMT status on WM memantine-sensitivity to be comparable to those for PPI (65% increase in effect size), then the estimated d for Val/Val vs. Met/Met sensitivity should be 1.20, and the proposed genotype subgroup sizes would yield power of 0.65 to detect genotype-sensitive memantine effects on WM.

Secondary "biomarkers" are MMN and GBS. For MMN, positive memantine effects will be detected by increased MMN amplitude at electrode Fz. For GBS, positive memantine effects would be detected by increased 40 Hz evoked power at electrode Fz. Unlike those for PPI, predictions of positive memantine effects on MMN and GBS are not based directly on previous findings from our laboratory, using measures identical to those proposed herein. However, based on reports in healthy subjects from other laboratories of memantine effects on MMN (d=0.87) and ketamine effects on GBS (d=0.69), the proposed 30 patients/dose group would yield power of 0.90 and 0.75, respectively, to detect positive memantine effects on these measures.

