The proposed study samples (Table 3) reflect both logistical and power consideration (see above, section "8. j. Statistics.") that differ across the several different studies covered by this application. Testing in the "ONE-DAY" session is designed for parametric "mini-studies", and the proposed sample of "up to 50 subjects" per year will allow us to study up to 5 different sets of stimulus parameters, with n's of 10 subjects per study. To study drug effects on PPI in normal control subjects, our target samples have historically been 20-30 subjects per dose; however, with the addition of COMT subgroup analyses, we currently plan to test 120 subjects in the within-subject amphetamine study, over a 2 year period (n=60/year). To study the effects of memantine on PPI and related measures in schizophrenia patients, we are proposing to study a total of 60 subjects: 30 per dose (10 and 20 mg). As this testing will be conducted over 2 - 3 years, we estimate recruitment needs of approximately 2 subjects per month, which will be easily accommodated by our recruitment capacity at the UCSD Medical Center, based on experience over the past 25 years.

Records and data will be rigorously protected, as described below. Aside from historical and questionnaire data, startle response, negative priming, MCCB, mismatch negativity and gamma band synchronization data will be obtained. Urine will be obtained for toxicological analysis as part of the subject exclusion process. Blood samples will be collected to identify genes that may be associated with PPI or its sensitivity to drugs.

The ethnic population in our male studies from the last 5 years (as we've only studied males exclusively based on drug study exclusion criteria) and is expected in the following years are:

Asian/Pacific Islander	29%
Black (not Hispanic)	3%
Hispanic	10%
White (not Hispanic)	56%
Other/unknown	2%

The ethnic population in our non-drug female studies from the last 5 years and is expected in the following years are:

Asian/Pacific Islander	12.5%
Black (not Hispanic)	2.5%
Hispanic	8.75%
White (not Hispanic)	72.5%
Other/unknown	3.75%

These numbers reflect the location of where we typically recruit subjects.

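### The genotype powers rest on 11 Val/Val and 7 Met/Met patients per dose group, counts that 30 patients per dose are not jointly expected to give unless patients are selected by genotype, and no selection rule is stated

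*Protocol*

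**What the plan says.** Aim 3 (Protocol section 6) assigns 60 schizophrenia patients to "placebo vs. 10 mg memantine (p.o.) (n=30) or placebo vs. 20 mg memantine (n=30) on two separate days". The power text in section 9, part j, adds "All analyses will be conducted independently for each dose group", so each genotype contrast draws on 30 patients; pooling of doses is kept for exploratory work.

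For PPI, the genotype effect is set at d = 1.53, the average of two control-subject effects (1.80 for low basal PPI and 1.27 for high novelty seeking), and the text concludes that "the proposed 11 Val/Val and 7 Met/Met patients/dose group would yield power of 0.90 to detect genotype-sensitive memantine effects". For WM it reasons that "the estimated d for Val/Val vs. Met/Met sensitivity should be 1.20" and that "the proposed genotype subgroup sizes would yield power of 0.65 to detect genotype-sensitive memantine effects on WM". Alpha is 0.05, with sidedness not given. Neither statement says where 11 and 7 come from.

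On selection, section 9, part e (Venopuncture) lets subjects be called back according to design needs after COMT typing. Its example is an "equal number of Met/Met, Val/Met and Val/Val allelic carriers", and memantine 20 mg is among the drugs named. The text specific to patients is silent: Aim 3 only has them characterized genetically, the section 11 eligibility criteria contain no genotype item, and section 10 plans 60 patients at 24 per year, adding "we estimate recruitment needs of approximately 2 subjects per month". Section 9.j warns, without numbers, that skewed allele frequencies might prevent detection of an interaction.

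**The concern.** A comparison of two homozygous groups is limited mainly by the smaller one. Genotype counts from unselected enrolment are tied together by the allele frequency, so more Val/Val means fewer Met/Met. The two planning counts look too large to come jointly from 30 such patients. If so, both genotype powers are too high even when the assumed effects are right. At stake is the credibility of the test of what section 9.j calls a critical moderator, including how a null interaction would be read.

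**Working it through.** **Inputs.** From section 9.j: 11 and 7 per dose group; d = 1.53 (PPI) and 1.20 (WM); alpha 0.05; as few as 24 per dose after the largest expected attrition. From Aim 3: 30 per dose. Assumed, because the documents give neither: Hardy-Weinberg proportions and the Val frequency p, which is varied.

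**Step 1: reproduce the stated powers.** For a two-group comparison of drug effect, the noncentrality is d × √(n1n2/(n1+n2)). With 11 and 7, n1n2/(n1+n2) = 77/18 = 4.28.

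| Method, 11 vs 7 | PPI, d = 1.53 (stated 0.90) | WM, d = 1.20 (stated 0.65) |
|---|---|---|
| Two-sided t, 16 df | 0.844 | 0.645 |
| Two-sided normal | 0.886 | 0.699 |
| One-sided t, 16 df | 0.916 | 0.767 |
| One-sided normal | 0.936 | 0.799 |

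The 0.90 is matched within two points by the two-sided normal or the one-sided t. The 0.65 is matched only by the two-sided t. No single method gives both.

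**Step 2: can both counts be expected from 30?** Expected counts are 30p² Val/Val and 30(1−p)² Met/Met. Having 11 and 7 together requires √(11/30) + √(7/30) = 0.606 + 0.483 = 1.089, but the two terms must sum to 1.

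- 11 Val/Val (p = 0.606) gives 30 × 0.394² ≈ 4.7 Met/Met.
- 7 Met/Met (p = 0.517) gives 30 × 0.517² ≈ 8.0 Val/Val.
- The allele frequency implied by 11/12/7 itself, p = (22 + 12)/60 = 0.567, gives about 9.6 and 5.6.
- The largest n1n2/(n1+n2) is at p = 0.5: 7.5 and 7.5, value 3.75, against 4.28 for 11 and 7.

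The smallest group from which both could be expected is (√11 + √7)² = 35.5, so 36 per dose.

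**Step 3: like-for-like loss, n = 30, p = 0.5 (the best case).**

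| Method | PPI: 11/7 → 7.5/7.5 | WM: 11/7 → 7.5/7.5 |
|---|---|---|
| Two-sided t | 0.844 → 0.782 | 0.645 → 0.576 |
| Two-sided normal | 0.886 → 0.842 | 0.699 → 0.642 |
| One-sided t | 0.916 → 0.877 | 0.767 → 0.711 |

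**Step 4: range, two-sided t.**

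| Val frequency | Counts, n = 30 | PPI | WM | Counts, n = 24 | PPI | WM |
|---|---|---|---|---|---|---|
| 0.5 | 7.5 / 7.5 | 0.78 | 0.58 | 6.0 / 6.0 | 0.67 | 0.47 |
| 0.606 | 11.0 / 4.7 | 0.73 | 0.52 | 8.8 / 3.7 | 0.61 | 0.42 |
| 0.7 | 14.7 / 2.7 | 0.58 | 0.40 | 11.8 / 2.2 | 0.48 | 0.32 |

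**The case against.** The strongest reply is that unselected enrolment is inferred. No section says patients are taken regardless of genotype, section 9.e permits genotype call-back, and the word proposed suits a target as well as an expectation. This stands in part: a reader might infer that the design cannot deliver 11 and 7, and the documents do not support that. With call-back the counts can be enrolled by design, and equal thirds (10/10/10) would give PPI power of 0.90 by two-sided t. But section 9.e is permissive and general, its equal-number example does not yield 11 and 7, and the patient text has no quota and no allowance for patients typed but not tested. The warning about skewed allele frequencies also fits better with counts left to chance.

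Second, the incompatibility depends on Hardy-Weinberg. Mixed ancestry adds homozygotes, and an observed 11/12/7 would not be anomalous (chi-square 1.03, p = 0.31). To expect that split, however, the inbreeding coefficient would have to be 1 − 12/14.73 = 0.19, for example two equal halves with Val frequencies of about 0.78 and 0.35.

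Third, setting 0.78 against the stated 0.90 suggests a 12-point loss. That mixes two things: by two-sided t, 11 and 7 already give only 0.844. For PPI the counts alone cost 4 to 6 points at the best frequency.

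Fourth, reaching at least 11 and at least 7 has a probability of at most about 7% per dose group, but this overstates the problem, because other splits serve as well (9/9 is better than 11/7). The chance of an n1n2/(n1+n2) of 4.28 or more is about 15% at p = 0.5.

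Finally, the protocol has fallbacks: separate subgroup ANOVAs, which it calls weaker, and pooling of doses. Pooling could give about 15/15 at p = 0.5, with power 0.98 at d = 1.53, but it is exploratory and conditional on similar dose effects. Neither fallback supports the powers quoted per dose group.

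**Conclusion.** The point holds in a conditional form. Given Hardy-Weinberg proportions and no genotype selection of patients, 11 and 7 are not jointly expected from 30 per dose, and the genotype powers are lower under every method and allele frequency tried. At best the loss is about 4 to 6 points for PPI and 6 to 7 for WM; it grows as the allele frequency moves from 0.5 or as patients drop out. The mismatch between the two stated powers is a separate matter and needs neither assumption.

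It would be too strong to say that the planned counts are unattainable, or that the design fails to provide them. What the documents show is that the source of the counts and any selection rule are missing. The consequence is confined to the COMT moderator hypothesis: the primary PPI test uses all 30 patients per dose, and the SAP contains no COMT analysis. The correction should still be made, because it is cheap and the stated powers are unsupported as they stand.

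**What to change.** In section 9.j, say whether the patient groups are selected by genotype.

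- **If not:** replace 11 and 7 with expected counts from a stated Val frequency, with a plausible range and a line for 24 evaluable patients. Restate both powers with one named test and its sidedness. By two-sided t these are at most about 0.78 (PPI) and 0.58 (WM) at n = 30, and at most 0.67 and 0.47 at n = 24.
- **If call-back is intended:** state the quota per dose group, compute power from it, and give the number of patients to be typed. To expect 11 and 7, at least 36 per dose must be typed even at the most favourable Val frequency (about 0.56); at 0.7 it is 7/0.09 ≈ 78. Section 10 should then carry that recruitment load.

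The first option costs protocol wording and less favourable stated powers. The second adds screening and typing.

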For example, to assess the effects of memantine on "gating" measures in schizophrenia patients, the primary measure will be evaluated by 2-way repeated-measure ANOVA of PPI with memantine dose and prepulse interval as within-subject factors. The hypothesis that memantine will increase PPI in schizophrenia patients will be confirmed by a significant effect of dose (active > PBO) or significant dose x interval (int) interaction and post-hoc comparisons at one or more prepulse intervals. Existing data (see above) provide a strong *a priori* prediction that the 120 ms prepulse interval will be most sensitive to PPI-enhancing effects of MEM. The effect size (d) for PPI-enhancement by 20 mg memantine in HCS was 0.91; with a similar "d" in patients, 30 patients/dose yields power of 0.92 to detect the predicted memantine effects; with maximum expected attrition (n=24), power is 0.85. Past findings also lead to the prediction that these MEM effects would be most robust in subjects exhibiting the lowest basal PPI levels (d=1.80). Using a median split of mean basal (screening) PPI levels, ANOVA as above will detect a significant interaction of memantine dose x basal PPI level, or dose x basal level x int, and significant post-hoc comparisons at one or more prepulse intervals (again, 120 ms being the strongest *a priori* candidate). Given the published "d" in control subjects, a comparable "d" in the proposed 12-15 "low PPI" patients/dose group would yield power >0.95 to detect the predicted memantine effects.

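### The fallback COMT test, a memantine effect in Val/Val but not Met/Met from separate ANOVAs, compares two significance results rather than two effects and does not control error for a genotype difference

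*Protocol*

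**What the plan says.** Aim 3 (Protocol section 6) includes the moderating role of genotype in the memantine effect in schizophrenia patients. Section 9, item j predicts that Val/Val patients will be the most sensitive and sets out two routes to test this.

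- **First route:** ANOVA with genotype between subjects and with dose and prepulse interval within subjects. "Significant genotype x dose or genotype x dose x int interactions, with appropriate post-hoc comparisons, would confirm the hypothesis".
- **Second route:** the protocol notes that factors such as skewed allele frequencies "might preclude detection of a significant 2- or 3-way interaction". For that case it provides a further analysis: "A secondary (albeit weaker) test of the hypothesis will utilize separate ANOVAs in Val/Val vs. Met/Met subgroups". The expected result is that memantine raises PPI in Val/Val patients and does not do so in Met/Met patients.

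On numbers, the plan states: "the proposed 11 Val/Val and 7 Met/Met patients/dose group would yield power of 0.90". That figure is for a genotype-dependent effect at an assumed d of 1.53. Also, "All analyses will be conducted independently for each dose group", so each route is run once at 10 mg and once at 20 mg. The SAP covers PPI, mismatch negativity and the auditory steady-state response and contains no COMT analysis. It neither repairs the second route nor carries it forward.

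**The concern.** The hypothesis is that one genotype responds more than the other, which is a statement about a difference. The second route never estimates or tests that difference. It asks whether one p-value falls below 0.05 while another does not. With the same true effect in both genotypes, that happens whenever the larger subgroup reaches significance and the smaller one misses it. Because Val/Val is the larger subgroup, the imbalance pushes towards the predicted answer.

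The route is kept for the situation in which the valid comparison has not shown a difference. What is at stake is a statement that memantine sensitivity depends on COMT genotype, made from data in which the genotypes may respond alike.

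**Working it through.** **Inputs.** Alpha 0.05 (section 9, item j); two-sided testing is assumed because sidedness is not stated. Subgroups of 11 and 7 per dose group. Common effect: "The effect size (d) for PPI-enhancement by 20 mg memantine in HCS was 0.91". Not in the documents, so assumed: the between-day correlation r of PPI (shown from 0 to 0.9) and any effect size for 10 mg.

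**1. The plan's own power figure.** For d = 1.53 with 11 vs 7, the noncentrality is 1.53 × √(11 × 7/18) = 3.16. The normal approximation gives Φ(3.16 − 1.96) = 0.886, and a one-sided t test gives 0.916. Both are close to the stated 0.90. The exact two-sided t test on 16 df gives 0.844. Nothing below depends on this figure.

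**2. Reading of d.** At d = 0.91 the two-sample formula gives power 0.934 (n = 30) and 0.870 (n = 24), near the stated 0.92 and 0.85. The paired formula with 0.91 as the standardised change gives 0.998 and 0.989. So d is read in raw SD units, and the standardised change is dz = d/√(2(1 − r)).

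**3. Pattern rate with equal true effects.** A two-level within-subject ANOVA is a paired t test, so

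P(pattern) = power(n = 11) × [1 − power(n = 7)], from the noncentral t.

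| r (d = 0.91) | dz | Power, 11 | Power, 7 | Pattern |
|---|---|---|---|---|
| 0 | 0.643 | 0.487 | 0.300 | 34% |
| 0.38 | 0.817 | 0.686 | 0.443 | 38% (peak) |
| 0.5 | 0.910 | 0.776 | 0.524 | 37% |
| 0.7 | 1.175 | 0.938 | 0.736 | 25% |
| 0.8 | 1.439 | 0.990 | 0.884 | 11% |
| 0.9 | 2.035 | 1.000 | 0.993 | 0.7% |

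Other common effects: d = 0.5 gives 16%, 26% and 38% at r = 0, 0.5 and 0.8; d = 1.53 gives 30%, 8% and 0.1%. With no drug effect the rate is 2.4%.

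**4. Role of the imbalance.** At dz = 0.91 the predicted pattern occurs in 37% of studies and its reverse in 12%. With 9 vs 9, each would occur in 22%.

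**5. After a non-significant interaction.** Simulated (300,000 runs) at d = 0.91, the pattern rate given a non-significant single-contrast interaction is 33%, 37%, 24%, 11% and 0.6% at r = 0, 0.5, 0.7, 0.8 and 0.9. A failed first route therefore hardly lowers it.

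**6. Prepulse interval included.** Simulated (40,000 runs) with five intervals and an assumed correlation of 0.3 or 0.6 between interval change scores. Support was a positive dose effect, or a dose × interval effect with a positive 120 ms comparison.

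| Common effect | r = 0 | r = 0.5 | r = 0.7 | r = 0.8 |
|---|---|---|---|---|
| 0.91 at every interval | 35–38% | 14–28% | 3–12% | 0.4–3% |
| 0, 0.1, 0.2, 0.5, 0.91 rising to 120 ms | 28–31% | 40–41% | 29–33% | 13–18% |

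**7. Comparator.** One direct genotype contrast of drug-minus-placebo change errs 2.5% of the time in the predicted direction, whatever the common effect. The protocol's first route accepts either of two interactions with post-hoc comparisons. Simulated with five intervals, either interaction is significant in some direction about 10% of the time. In the predicted direction the error is about 3 to 4%.

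**The case against.** **The protocol already subordinates this route.** It attaches confirmation only to the interaction and calls the separate ANOVAs secondary and weaker. That stands, and it limits the consequence. A reader might infer that the separate ANOVAs can confirm moderation or override a non-significant interaction; no sentence says so. But the route is still labelled a test of the hypothesis, and calling it weaker suggests less power. It does not tell the reader that equal response can produce the predicted pattern often.

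**No live consequence is shown.** A reader might infer that a spurious genotype finding was reported. The SAP describes completed analyses and none involves COMT, so the documents do not support that.

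**The 38% is a peak from a simplified model.** This is correct. A reader might take it as the error rate of the plan, but it needs r near 0.38 at d = 0.91, and the planned ANOVA includes prepulse interval. The only indirect clue to r is a pilot F of 10.68 in 8 subjects (Protocol section 8), and the caption leaves unclear which measure it belongs to. If it is working memory (d = 0.73), dz = √(10.68/8) = 1.155 and r = 1 − (0.73/1.155)²/2 = 0.80. If PPI behaved alike, the paired-model rate would be 11%, which is still well above 2.5%.

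**The regression in the same paragraph.** "Logistic regressions might be used, with genotype coded to reflect" allele count might look like a further moderation test, or like the place for a repair. It is offered only to describe how the measures are distributed, so it has no part in this point.

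**Conclusion.** The point holds for the fallback test. Separate subgroup ANOVAs do not control error for a genotype difference, and the 11 vs 7 split favours the predicted result. With equal response, the paired model at d = 0.91 gives 34–38% for r from 0 to 0.5, 25% at 0.7, 11% at 0.8 and under 1% at 0.9. With prepulse interval modelled, the examples span 0.4% to 41%. The comparison is 2.5% for a single direct contrast, or about 3 to 4% for the protocol's interaction rule.

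These sizes rest on assumed values of r, on the healthy-control d, on two-sided tests and, in step 6, on assumed correlations between intervals. The rate is small when power is very low in both subgroups or very high in both. Separate analysis of the two doses gives the pattern two chances to appear; that is not counted above. The primary PPI hypothesis is not touched. The change should be made because it governs what may be concluded about a named Aim 3 objective.

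**What to change.** - Do not count the separate-ANOVA pattern as a test of, or evidence for, genotype moderation. Present the Val/Val and Met/Met effects as descriptive.
- Report the difference between the two effects with a 95% confidence interval. At 11 vs 7 its half-width is about t(0.975, 16 df) × √(1/11 + 1/7) = 2.12 × 0.483 = 1.02 SD of change.
- Base any genotype conclusion on the genotype × drug interaction that the protocol already ranks first.

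The cost is a change of wording and one extra interval, with no new data. The interval will be wide, and a non-significant interaction will remain inconclusive rather than being rescued by subgroup p-values. Since the SAP reports finished analyses, anything added now should be labelled post hoc.
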